This statistical analysis plan (SAP) documents the statistical methodology and data analysis algorithms and conventions to be applied for statistical analysis and reporting of efficacy, safety, and pharmacodynamic data of Trial 156-12-298. All amendments to the protocol are taken into consideration in developing this SAP.

2 Trial Objectives

The primary objective is to evaluate the long term safety effects of treatment with tolvaptan in a pediatric and adolescent Autosomal Dominant Polycystic Kidney Disease (ADPKD) population.

The secondary objective is to assess the pharmacodynamics (PD), pharmacokinetics (PK), and efficacy of tolvaptan in children and adolescent subjects with ADPKD.

3 Trial Design

3.1 Type/Design of Trial

The trial will comprise 2 phases as described below:

Phase A is a randomized, double-blind, placebo-controlled phase to compare tolvaptan with placebo. The duration of treatment is 12 months. It is open to subjects between the ages of 4 and 17 years, inclusive. Subjects between the ages of 12 and 17 years will be stratified by age and gender. When these stratified cohorts have been closed, enrollment for the trial will end ([Figure 3.1-1](#)). Additionally, subjects aged 4 to 11 years may be eligible for participation following discussion with the medical monitor.

Qualified subjects who complete Phase A may continue into Phase B. A qualified subject is defined as one who is willing to continue in the trial and who does not have any AEs that would require investigational medicinal product (IMP) discontinuation.

[figure not shown]
Phase B is an open-label phase during which subjects who have completed Phase A of the trial will receive treatment with tolvaptan for 24 months ([Figure 3.1-2](#)).

When all subjects in Phase A have either completed the Month 12 visit or early terminated from the trial, a snapshot of the data will be taken. At that time, the snapshot will be unblinded, and results analyzed and reported in an interim clinical study report

[figure not shown]
Protocol 156-12-298

(CSR) to provide early information on safety. The protocol may be amended to further ensure continuing safety and tolerability measures are in place.

When all subjects in Phase B either complete the Month 24 visit, or the last ongoing subject terminates early, the database will be locked, and a final CSR will be provided to the regulatory authorities.

Figure 3.1-1 Trial Design Schematic Phase A, Randomized, Double-blind

^aSubjects between the ages of 4 and 11 are eligible for the trial but are not included in the age cohorts.

Figure 3.1-2 Trial Design Schematic Phase B, Open-Label

3.2 Trial Treatments

Tolvaptan will be provided as 7.5, 15, and 30 mg spray-dried, immediate-release tablets with matching placebo. Tolvaptan will be administered as a split-dose, with the first dose taken upon awakening and the second dose taken approximately 8 hours later.

3.2.1 Treatment in Phase A

Subjects will be randomized to receive IMP defined as either active tolvaptan or matching placebo for 12 months. Starting doses will be based on weight as denoted below in [Table 3.2.1-1](#).

After 1 week, subjects who have tolerated their initial dose will up-titrate once from their starting dose ([Table 3.2.1-2](#)). Subjects may down-titrate at any time during the trial, however subjects will be asked to stay on the highest tolerable dose (by weight group) if possible ([Table 3.2.1-3](#)).

It is recommended that each dose be administered with 240 mL of water, as part of the goal to maintain proper hydration status; the total 240 mL can be consumed over a 1-hour period following dosing. Water intake will be recorded for all in-clinic dosing.

Table 3.2.1-1 Starting Tolvaptan Dose

Body Weight	Time	Split-dose ^a
≥ 20 kg to < 45 kg	Upon awakening / 8 hours later	15/7.5 mg TLV or matching placebo
≥ 45 kg to ≤ 75 kg	Upon awakening / 8 hours later	30/15 mg TLV or matching placebo
> 75 kg	Upon awakening / 8 hours later	45/15 mg TLV or matching placebo

TLV = tolvaptan.

^a Split-dosing will be twice daily dosing with the larger dose taken upon awakening and the smaller dose taken approximately 8 hours later.

Doses may be titrated down dependent upon subject tolerability.

Table 3.2.1-2 Up-titration Steps

Current Dose	Up-titrated Dose	Body Weight
15/7.5 mg TLV or matching placebo	30/15 mg	≥ 20 kg to < 45 kg
30/15 mg TLV or matching placebo	45/15 mg	≥ 45 kg to ≤ 75 kg
45/15 mg TLV or matching placebo	60/30 mg	> 75 kg

Protocol 156-12-298

Table 3.2.1-3	Down-titration Steps
Current Dose	Down-titrated Dose
7.5 mg once daily upon awakening	Subject to be withdrawn from IMP
7.5/7.5 mg	7.5 mg once daily upon awakening
15/7.5 mg	7.5/7.5 mg
22.5/15 mg	15/7.5 mg
30/15 mg	22.5/15 mg
45/15 mg	30/15 mg
60/30 mg	45/15 mg

Subjects should attempt to complete 7 days of dosing between down-titration steps to provide the best opportunity for a subject to be given their maximally tolerated dose.

3.2.1.1 Dosing for Dense PK and PD Sampling

A subset of 20 subjects, half on tolvaptan and half on placebo, in the 12 to 17 year old age group will have dense PK sampling after at least 1 month on IMP. The blind will be maintained by utilizing the Interactive response system (IXRS) to determine how many subjects on tolvaptan or placebo have been assessed and closing a group when 10 subjects have completed. The doses that the subjects will be given will be from their currently prescribed IMP. The morning dose will be administered at approximately 8:00 AM in the fasting state (no food within 8 hours prior to dosing or within 2 hours postdosing), the afternoon dose 8 hours later, and with dinner served at least 2 hours postdose. Each dose will be administered with 240 mL still, room temperature water; the total 240 mL can be consumed over a 1-hour period following dosing.

3.2.2 Treatment in Phase B

Subjects who have completed Phase A on treatment and continue in Phase B will receive open-label tolvaptan for up to 24 months. In order to preserve the blind in Phase A, subjects will be started at a dose based on their current body weight (see [Table 3.2.1-1](#)) and after 1 week, they will be asked to up-titrate once from their starting dose. Subjects who wish to lower their dose secondary to tolerance will have their doses adjusted as necessary.

3.3 Trial Population

The target trial population will be at least 60 male and female subjects aged 12 to 17 years (inclusive), with a diagnosis of ADPKD as defined by the presence of family history and/or genetic criteria AND who have at least 10 renal cysts, each of which measures at least 0.5 cm confirmed upon magnetic resonance imaging (MRI) inspection. In accordance with the PIP requirements, the trial will also allow subjects aged 4 to 11 years who meet criteria for entry to be enrolled concurrently during the recruitment

Protocol 156-12-298

period for the target population. It is expected that the trial may enroll approximately 100 subjects.

Subjects who are MRI-naive or under the age of 12 should have at least 4 cysts that are at least 1 cm in size confirmed by ultrasound prior to MRI inspection.

Treatment groups for the required population will be stratified by age and gender in the following age cohorts:

- Female subjects ages 12 to 14 years, inclusive
- Female subjects ages 15 to 17 years, inclusive
- Male subjects ages 12 to 14 years, inclusive
- Male subjects ages 15 to 17 years, inclusive

When > 15 subjects are enrolled in an age cohort, new screening for that age cohort will be closed; subjects concurrently in screening for that age cohort may be enrolled if they meet inclusion/exclusion criteria. When the last subject in the final age cohort for the required population has been achieved, enrollment in the trial will cease.

The trial is also open to children between the ages of 4 to 11 years (inclusive) with ADPKD, who meet the above criteria and who, in the opinion of the investigator, would benefit from treatment. Subjects, aged 4 to 11 years (inclusive), must have an ultrasound to assess renal cysts.

Qualified subjects who complete Phase A are eligible to participate in Phase B.

4 Sample Size

A sample size of at least 60 subjects from 12 to 17 years of age inclusive is proposed for the Phase A of this trial. It is expected that the trial may enroll approximately 100 subjects in total. Since the data collected will be summarized using descriptive statistics and not aimed at testing a specific hypothesis, no formal power calculations are undertaken.

5 Statistical Analysis Datasets

5.1 Analysis Datasets

The following analysis sets are defined for the efficacy and safety analysis in this trial.

Randomized: It consists of all subjects who were randomized in the trial.

Protocol 156-12-298

Full Analysis Set (FAS) for Phase A consists of all subjects who have been randomized to a treatment group, received at least 1 dose of the IMP, have both a Phase A baseline and at least 1 post-baseline efficacy evaluation. They will be analyzed according to the treatment group to which they were randomized. FAS for Phase B consists of all subjects who enrolled to Phase B, received at least 1 dose of the IMP, have both a baseline and at least 1 post-baseline efficacy evaluation in Phase B. The FAS, which is based on intent-to-treat principle, will be the primary analysis set for efficacy analyses on the primary/key secondary endpoints and other secondary endpoints.

Safety Analysis Set (SAS): It consists of all subjects who were administered at least 1 dose of IMP. The safety dataset will be used for safety analyses. The safety datasets for each phase are defined as:

- I. Phase A Safety Set: All subjects who randomized and receive at least one dose of IMP in Phase A.
- II. Phase B Safety Set: All subjects who are enrolled into Phase B and receive at least one dose of IMP in Phase B.

5.2 Handling of Missing Data

All safety/efficacy data will be summarized for observed (non-missing) values only. Missing data will be mitigated by encouraging subjects who withdrew from treatment to return for their remaining visits for collection of assessments as noted in the Schedule of Assessments, [Table 3.7-1](#) for Phase A and [Table 3.7-2](#) for Phase B, in protocol.

6 Trial Conduct

In general, analyses methods stated in [Section 6](#) to [Section 9](#) will apply to Phase A and Phase B unless otherwise specified. In the final CSR, Phase A and Phase B will be reported separately unless otherwise specified.

6.1 Subject Disposition

The number of subjects who have been randomized, the number of subjects who are treated, and the number of subjects who discontinue from the trial, together with the reasons for discontinuation taken from the case report form (CRF) status page will be provided.

Protocol 156-12-298

6.2 Treatment Compliance

Treatment compliance will be calculated by dividing the total dosage taken by the total dosage the subjects are scheduled to take during the treatment phase based on the Study Medication panel of CRF.

6.3 Prior and Concomitant Medications

Use of concomitant medications prior to the start of trial medication will be summarized by number and percentage of users by treatment group.

Concomitant medications used post-baseline will be summarized in two categories of time interval: during the trial medication period and after the trial medication period. In each case, the use of concomitant medications will be summarized by number and percentage of users by treatment group.

6.4 Protocol Deviations

Major protocol deviations data will be summarized by type of deviations (eg, deviations in entry criteria, dosing, randomization, concomitant medication, procedural, etc) by center and treatment group. In addition, a subject listing will be provided describing the deviations for each subject.

7 Demographic and Baseline Characteristics

Demographic characteristics and medical history at screening will be summarized by descriptive statistics, eg, proportion, mean, median, SD, minimum and maximum values.

Baseline characteristics will be summarized for Treatment Phase A and Treatment Phase B, respectively.

For the Randomized Sample, baseline disease evaluation will be summarized by treatment group and overall with the mean, median, range and standard deviation presented.

8 Primary and Secondary/ Exploratory Endpoints Analyses

8.1 Primary Endpoint Analysis

The co-primary endpoints for the trial are the change from Phase A baseline in spot urine osmolality (premorning dose) and specific gravity (premorning dose) to Week 1.

Two variables will be derived for the co-primary outcomes:

- Change from Phase A baseline in spot urine osmolality (premorning dose) to Week 1
- Change from Phase A baseline in specific gravity (premorning dose) to Week 1

Protocol 156-12-298

Descriptive statistics will be presented on the co-primary endpoints by treatment group, respectively.

Baseline measurements of co-primary efficacy variables are defined as their last measurements prior to the first dose of trial medication in Phase A.

8.2 Key Secondary Endpoint Analysis

The key secondary endpoint is the percent change from Phase A baseline in height-adjusted total kidney volume (htTKV) as measured at 12 months.

Descriptive statistics will be presented on the key secondary endpoint by treatment group.

Baseline measurements of key secondary efficacy variable is defined as its last measurement prior to the first dose of trial medication in Phase A.

8.3 Other Secondary Endpoints Analyses

Other secondary efficacy endpoints include:

- 24-hour fluid balance prior to Week 1.
- Change from baseline in renal function (eGFR by Schwartz formula) at each clinic visit (Week 1, Month 1, Month 6, and Month 12 in Phase A).
- Change from baseline in renal function (eGFR by Schwartz formula) at each clinic visit (Week 1, Month 1, Month 6, Month 12, Month 18, and Month 24 in Phase B).
- Percent change in htTKV as measured by MRI from Phase B baseline to Phase B Month 12.
- Percent change in htTKV as measured by MRI from Phase B baseline to Phase B Month 24.
- Pharmacodynamic (PD) endpoints of urine volume (including 24-hour fluid volume), fluid intake and fluid balance, sodium, creatinine, and free water clearance during dense PK sampling (after at least 1 Month on IMP).
- Proportions of each Tanner Stage by gender and age compared to normative populations at baseline, 6 months, and 12 months during the placebo-controlled phase (Phase A), and every 6 months during the open-label extension phase (Phase B).
- Changes from baseline percentiles for height and weight by gender and age at baseline, 6 months, and 12 months during the placebo-controlled phase (Phase A), and every 6 months during the open-label extension phase (Phase B).
- Safety variables (changes from baseline in creatinine, vital signs, laboratory values including liver function tests [LFTs], rate of aquaretic AEs) in placebo and tolvaptan.

For all of the secondary endpoints in Phase A, descriptive statistics by visit will be presented by treatment group. For the secondary endpoints in Phase B, descriptive

Protocol 156-12-298

statistics will be presented by previous Phase A treatment group (Tolvaptan and placebo) and pooled.

The formula for eGFR by Schwartz¹ is:

$$\text{eGFR} = 0.413 \times \text{height [cm]} / \text{serum creatinine [mg/dL]}$$

To account for the hemodynamic effects of Tolvaptan, the analysis for change of eGFR in Phase A will be provided using week 1 as baseline as supplemental analysis.

9.1 Extent of Exposure

A subject's duration of exposure is defined as the trial medication end date - trial medication start date + 1 in each phase. Duration of exposure will be summarized by

Protocol 156-12-298

treatment group in Phase A and by previous Phase A treatment group (Tolvaptan and placebo) and pooled in Phase B.

9.2 Adverse Events

All adverse events (AE) will be coded by MedDRA System Organ Class (SOC) and Preferred Term (PT). A treatment-emergent AE (TEAE) is defined as an AE which starts after start of trial medication), or an AE continues from baseline of the specific phase and becomes serious, worsening, trial drug-related or results in death, discontinuation, interruption or reduction of trial medication during this phase. The incidences of the following treatment-emergent adverse events (TEAEs) will be summarized by treatment groups:

- TEAEs by severity
- Potentially drug-related TEAEs
- TEAEs with an outcome of death
- Serious TEAEs
- Discontinuations due to TEAEs

Incidences of AEs above will be tabulated by treatment for Phase A safety dataset and Phase B safety dataset, respectively.

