
Investigational Medicinal Product(s), Dose, Dosage regimen, Treatment period, Formulation, Mode of Administration:
	
Tolvaptan will be provided as 7.5, 15, and 30 mg spray-dried, immediate-release tablets with matching placebo.
 
Tolvaptan will be administered as a split-dose, with the first dose taken upon awakening and the second dose taken approximately 8 hours later.
 
Subjects will be randomized to receive IMP defined as either active tolvaptan or matching placebo for 12 months. Starting doses will be based on weight:
 
 • ≥ 20 kg to < 45 kg, 15/7.5 mg TLV split-dose or matching placebo • ≥ 45 kg to ≤ 75 kg, 30/15 mg TLV split-dose or matching placebo • > 75 kg, 45/15 mg TLV split-dose or matching placebo 
After 1 week, subjects will be asked to up-titrate once from their starting dose.
 
 • ≥ 20 kg to < 45 kg, 30/15 mg TLV split-dose or matching placebo • ≥ 45 kg to ≤ 75 kg, 45/15 mg TLV split-dose or matching placebo • > 75 kg, 60/30 mg TLV split-dose or matching placebo 
Subjects may down-titrate at any time during the trial, however subjects will be asked to stay on the highest tolerable dose (by weight group) if possible.
 
It is recommended that each dose be administered with 240 mL of water, as part of the goal to maintain proper hydration status; the total 240 mL can be consumed over a 1-hour period following dosing.

Trial Assessments:
	
Efficacy:
 
 • Total kidney volume assessed by MRI or ultrasound • Assessment of renal function (eGFR by Schwartz formula) 
Pharmacokinetic:
 
 • PK blood samples - sparse sampling and dense sampling in a subset of subjects 
Pharmacodynamic:
 
 • Urine osmolality and specific gravity • 24-hour fluid balance • Serum sodium, creatinine, and osmolality • Urine volume and urine sodium, creatinine, and osmolality

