1.3 Known and Potential Risks and Benefits

ADPKD is a devastating, progressive disease that places a tremendous burden on patients and their families. The risk which a patient is willing to accept is a personal decision based on his/her individual and familial experience with the disease.

The most common observed risks of tolvaptan therapy in adults include those arising from aquaresis (eg, polyuria, pollakiuria, nocturia, thirst, dry mouth), dehydration, electrolyte abnormalities, and gout. While aquaretic events did not contribute to significant subject morbidity over 3 years of study in the pivotal placebo-controlled trial (Trial 156-04-251), they do represent adverse drug reactions which occur early (within days to weeks) and are most likely to limit a subject's ability to continue therapy over a duration of treatment that is likely to provide benefit. While the proposal of increased water ingestion as a mechanism of ameliorating CKD⁹ has not reached medical equipoise, in this trial we believe a general recommendation to do so is reasonable and would recommend ingestion of water adequate to avoid thirst.

The most notable safety issue associated with chronic tolvaptan use, newly identified in Trial 156-04-251, is the potential for idiosyncratic hepatic toxicity. With a once every 4 month monitoring scheme, an imbalance in the proportion of subjects with elevated transaminases (tolvaptan > placebo) led to identification of 3 subjects (total from both Trial 156-04-251 and its open-label extension trial, 156-08-271) with laboratory and clinical evidence of potentially serious drug-induced liver injury (DILI). Based on the available data from the aforementioned trials, the sponsor proposed that appropriate subject monitoring and management be implemented to mitigate this potential risk in the ADPKD population. For this trial, standard liver parameters will be measured at baseline and then monthly thereafter.

Significant events related to glaucoma and skin neoplasms were also observed; however the causal relationship to tolvaptan remains uncertain. These adverse events (AEs) and the above attributable adverse reactions should be considered in light of the benefits of a reduced risk of ADPKD kidney complications, including renal pain, urinary tract infection, hematuria, anemia, and nephrolithiasis.¹⁰

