Body Weight (kg)	Up-titrated morning dose (mg)	Up-titrated morning dose (mg/kg)	
		maximum	minimum
Adult			
40.6 to 133.6	60	1.48	0.45
Pediatric			
20 to <45	30	1.50	>0.67
45 to 75	45	1.00	0.60
>75	60	0.80	<0.80

Subjects who are unable to tolerate the initial starting dose regimen will be allowed to down-titrate to a dose as low as 7.5 mg once daily. This will allow for the collection of the most information on tolerability, safety, and potentially efficacy as the minimally effective dose of tolvaptan has not been determined. Animal studies indicated a dose response in tolvaptan efficacy with lower doses is still better than placebo. Adults in the pivotal 156-04-251 trial were titrated up in order to maximize inhibition of AVP but efficacy was observed in subjects who down-titrated to 45/15 mg and 60/30 mg regimens. In the phase 2 156-04-250 trial, subjects on the fixed regimen of 45/15 mg showed less efficacy when compared to subjects on 60/30 mg; however, both groups showed slower increase in TKV when compared to a matched control group.^{8,11}

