3.2.1 Phase A

Subjects will be randomized to receive IMP defined as either active tolvaptan or matching placebo for 12 months. Starting doses will be based on weight as denoted below in [Table 3.2.1-1](#).

After 1 week, subjects who have tolerated their initial dose will up-titrate once from their starting dose ([Table 3.2.1-2](#)). Subjects may down-titrate at any time during the trial, however subjects will be asked to stay on the highest tolerable dose (by weight group) if possible ([Table 3.2.1-3](#)).

It is recommended that each dose be administered with 240 mL of water, as part of the goal to maintain proper hydration status; the total 240 mL can be consumed over a 1-hour period following dosing. Water intake will be recorded for all in-clinic dosing.

Table 3.2.1-1 Starting Tolvaptan Dose

Body Weight	Time	Split-dose ^a
≥ 20 kg to < 45 kg	Upon awakening / 8 hours later	15/7.5 mg TLV or matching placebo
≥ 45 kg to ≤ 75 kg	Upon awakening / 8 hours later	30/15 mg TLV or matching placebo
> 75 kg	Upon awakening / 8 hours later	45/15 mg TLV or matching placebo

TLV = tolvaptan.

^aSplit-dosing will be twice daily dosing with the larger dose taken upon awakening and the smaller dose taken approximately 8 hours later.

Doses may be titrated down dependent upon subject tolerability.

Table 3.2.1-2 Up-titration Steps

Current Dose	Up-titrated Dose	Body Weight
15/7.5 mg TLV or matching placebo	30/15 mg	≥ 20 kg to < 45 kg
30/15 mg TLV or matching placebo	45/15 mg	≥ 45 kg to ≤ 75 kg
45/15 mg TLV or matching placebo	60/30 mg	> 75 kg

Table 3.2.1-3 Down-titration Steps	
Current Dose	Down-titrated Dose
7.5 mg once daily upon awakening	Subject to be withdrawn from IMP
7.5/7.5 mg	7.5 mg once daily upon awakening
15/7.5 mg	7.5/7.5 mg
22.5/15 mg	15/7.5 mg
30/15 mg	22.5/15 mg
45/15 mg	30/15 mg
60/30 mg	45/15 mg

Subjects should attempt to complete 7 days of dosing between down-titration steps to provide the best opportunity for a subject to be given their maximally tolerated dose.

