3.7.1.1.9 Dosing and Titration Considerations

Subjects may be titrated down for tolerability at any time during the trial according to the titration schedule in [Table 3.2.1-3](#). This titration may be done over the phone or in the clinic based on the investigator's judgment, although it is recommended that the subject be brought into the clinic if possible.

Planned drug interruptions are discouraged during the first month of dosing in Phase A and within the month prior to any MRI or ultrasound assessments. Refer also to [Section 3.8.3.3](#) for additional information on drug interruption and drug discontinuation.

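### The only adverse-event table by action taken with study drug counts discontinuations; TEAEs that led to dose reduction or interruption are not tabulated by arm

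*SAP*

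**What the plan says.** **Adverse-event tables.** SAP 9.2 summarises TEAEs by severity, by potential relation to drug, by fatal outcome and by seriousness, and adds "Discontinuations due to TEAEs". Protocol 7.9.1 adds a line for all TEAEs and otherwise matches it. In both lists, discontinuation is the only action taken with IMP that gets a line.

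**Where reduction and interruption do appear.** SAP 9.2 uses them once, in the TEAE definition. An event continuing from the phase baseline becomes treatment-emergent if, among other things, it results in "discontinuation, interruption or reduction of trial medication during this phase". No table is attached to that wording.

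**How intolerance is handled.** Protocol 3.2.1 states: "Subjects may down-titrate at any time during the trial". Section 3.7.1.1.9 gives the purpose: "Subjects may be titrated down for tolerability at any time during the trial". Section 2.2 lets subjects who cannot tolerate the starting regimen "down-titrate to a dose as low as 7.5 mg once daily" and says this maximises what is learned about tolerability. In Table 3.2.1-3, repeated in SAP 3.2.1, the step below that lowest dose reads "Subject to be withdrawn from IMP". Protocol 3.8.3.1 expects that subjects may have one or more interruptions.

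**Aquaretic events.** Protocol 1.3 singles these out as the reactions most likely to stop a subject staying on therapy. Their rate in placebo and tolvaptan is a secondary endpoint (Protocol 3.5.2, SAP 8.3) and a standard safety variable (Protocol 7.9, SAP 9).

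**The concern.** Tolerability is in the trial's title. The trial is descriptive, so its tolerability conclusion will be whatever the tables show. A subject who steps down several times because of polyuria but keeps taking some drug does not appear in the one table keyed to drug action. If the event was reported as an AE, that subject does count in the aquaretic rate and the severity table. Neither of those separates an event tolerated at full dose from one that forced a reduction.

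What is at stake is the difference between arms in events that limited dosing. Phase A uses matching placebo, so that comparison is randomised and blinded. The Phase A snapshot is meant to give early safety information, and Protocol 3.1 says the protocol may be amended afterwards on safety and tolerability grounds. Dose-limiting events by arm bear directly on that decision.

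**Working it through.** The plan states no figure to reproduce: Protocol 7.1 and SAP 4 say that no power calculation was done. The check is a count of steps, followed by a comparison of the planned outputs.

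**Step 1. Length of the down-titration ladder.** The top of the ladder is given in the Protocol Synopsis: "> 75 kg, 60/30 mg TLV split-dose or matching placebo". Following Table 3.2.1-3 down from there gives:

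60/30 → 45/15 → 30/15 → 22.5/15 → 15/7.5 → 7.5/7.5 → 7.5 mg once daily → withdrawn from IMP.

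Reduced regimens available before withdrawal, counted from each weight group's doses (Tables 3.2.1-1 and 3.2.1-2):

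| Weight group | From starting dose | From up-titrated dose |
|---|---|---|
| 20 to < 45 kg | 15/7.5: 2 | 30/15: 4 |
| 45 to 75 kg | 30/15: 4 | 45/15: 5 |
| > 75 kg | 45/15: 5 | 60/30: 6 |

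The range is 2 to 6. A subject who has already stepped down has fewer left.

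**Step 2. Summaries by action taken.**

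| TEAE led to | SAP 9.2 | Protocol 7.9.1 |
|---|---|---|
| Discontinuation | 1 | 1 |
| Dose reduction | 0 | 0 |
| Interruption | 0 | 0 |

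**Step 3. Could another planned output supply the missing counts?**

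- *Exposure (SAP 9.1)* is end date minus start date plus 1. Interruptions are not subtracted and dose level is not summarised.
- *Compliance (SAP 6.2)* is dosage taken over dosage scheduled. The SAP does not say whether the schedule is reset after down-titration. If it is, a subject on the lowest dose can show full compliance. Either way, the ratio is not linked to an AE.
- *Disposition (SAP 6.1)* counts discontinuations from the trial.
- *Summaries by total daily dose (SAP 10)* cover the dense-sampling subset of 20 subjects and are not AE tables.
- *Rate of aquaretic AEs (SAP 8.3 and 9)* is compared between arms but not split by action taken.
- *TEAEs by severity (SAP 9.2)* uses a functional scale (Protocol 5.1), which does not record whether the dose changed.

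None gives the number of subjects per arm with a TEAE leading to reduction or interruption.

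**Step 4. Is the information available?** The TEAE definition in SAP 9.2 cannot be applied without knowing whether an event led to reduction or interruption. Protocol 9.2 requires the action taken for each AE in the progress notes, from which the eCRF is completed. The footnotes to Tables 3.7-1 and 3.7-2 have the current dose recorded at each visit.

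**Step 5. Scale.** The required 60 subjects aged 12 to 17, randomised 1:1, give 60 / 2 = 30 per arm. Each subject is then 1 / 30 = 3.3 percentage points. If the total reaches about 100, arms are about 50 and each subject is 1 / 50 = 2 points. At these sizes, a few subjects moved from one drug-action category to another visibly change a descriptive comparison.

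**The case against.** The strongest case against is that the plan already reports aquaretic harm. The rate by arm is a named secondary endpoint, and a child with reported polyuria would also be in the severity table, and in the drug-related table if judged related. No endpoint or estimate is wrong, and the trial tests no hypothesis. On this view only one cross-classification is missing, event by dose action. That is a fair description of the gap, and it limits the weight of the point.

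A reader might infer three stronger things, and the documents support none of them:

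- *A subject must work down the whole ladder before being counted.* Down-titration is permitted, not required, and the 7 days between steps is something to attempt. Protocol 3.8.3.2 and 3.8.3.3 let a subject stop because of an AE at any dose, including one that is merely uncomfortable.
- *The discontinuation table will be nearly empty by design.* No discontinuation rate is given, and Protocol 1.3 expects aquaretic reactions to limit continuation in some subjects.
- *Aquaretic events go unreported.* They are reported, but not by whether they changed dosing.

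Two practical objections also stand. Neither document defines a list of aquaretic terms; Protocol 1.3 gives examples only. And a lower dose recorded at a visit does not show that an AE caused the reduction, since Protocol 3.2.2 lets subjects lower the dose at their own wish for tolerance. Both are met in the fix.

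Finally, the exploratory endpoint text is redacted, so a dose-change summary there cannot be ruled out. The safety lists themselves show no redaction.

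**Conclusion.** The point holds as a reporting gap. Among summaries by action taken, both documents list discontinuation alone, while the protocol gives subjects 2 to 6 reduced regimens, or an interruption, as alternatives to stopping. No unredacted output shows by arm how many subjects had a TEAE that led to either. The discontinuation table read alone can therefore understate dose-limiting intolerance. The size of any understatement cannot be stated, because the documents give no rates for reduction, interruption or discontinuation.

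The conclusion assumes that the redacted exploratory text contains no such table. The low cost assumes that action taken is held in the AE data, as the TEAE definition implies. No stated number changes. Label: cheap improvement.

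**What to change.** Add two lines to the list in SAP 9.2:

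- *TEAEs leading to dose reduction*
- *TEAEs leading to interruption of IMP*

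Present each overall and for a prespecified list of aquaretic preferred terms, by treatment group in Phase A, and by previous Phase A group and pooled in Phase B. Take attribution from the AE action-taken information and use the visit dose records only as a cross-check. Put the preferred-term list in a SAP appendix; the same list would also define the aquaretic AE rate already planned.

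The cost is two extra tables and a short term list. No new data, protocol amendment, dose change or clinical rule is needed.
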